6.1.2 Subjects to Analyze

Safety population will include all subjects who are enrolled and received at least one confirmed dose of IP. This population will be used for all safety analyses.

The Intention-to-Treat (ITT) population will include all randomized subjects. This population will be the primary analysis population for the analysis of efficacy endpoints.

Per-Protocol (PP) Population will include all subjects who are in the safety population, were at least 80% compliant with IP application, and showed no other serious deviations from the study protocol. This population will be used as a sensitivity analysis of primary and secondary efficacy endpoints.

The PK population will include all subjects receiving the active drug with sufficient plasma concentrations of roflumilast to define a profile, as determined by the pharmacokineticist. This population will be used for analyses of PK parameters.

6.1.3 Interim Analysis

One interim futility analysis is planned when the first 60 subjects randomized have had the opportunity to complete the 8 week disease assessment. This futility analysis will be non binding and will be used for decision making on further expansion and timing of the clinical development program in seborrheic dermatitis. Accrual to this study will not be held during the conduct and interpretation of this futility analysis. To maintain the integrity of the remaining

data to be collected, only sponsor staff responsible for planning further development in the seborrheic dermatitis program will be provided with results. This futility analysis will use a stopping rule defined by the rho family with parameter = 0.1.

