Study Endpoints	 The Primary Efficacy Endpoint will be defined as: Achievement of an IGA score of 'clear' or 'almost clear' PLUS a 2-grade improvement from Baseline at week 8

	The Secondary Efficacy Endpoints will include:
	• Achievement of an IGA score of 'clear' or 'almost clear' PLUS a 2-grade improvement from Baseline
	at weeks 2 and 4
	 Change from Baseline in Overall Assessment of
	Erythema score at weeks 2, 4, and 8
	• Change from Baseline in Overall Assessment of
	Scaling score at weeks 2, 4, and 8
	• Achievement of an Overall Assessment of Erythema
	(0-3 scale) score of 0 or 1 PLUS a 2-grade
	improvement from Baseline at weeks 2, 4, and 8
	• Achievement of an Overall Assessment of Scaling
	(0-3 scale) score of 0 or 1 PLUS a 2-grade
	improvement from Baseline at weeks 2, 4, and 8
	• Change in WI-NRS pruritus score at weeks 2, 4, and
	8, as compared to Baseline
	• In subjects with a Baseline WI-NRS pruritus score
	of \geq 4, achievement of a \geq 4-point improvement from
	Baseline in WI-NRS pruritus score at weeks 2, 4,
	and 8. Exploratory Endpoints will include:
,	 Change in Scalpdex total score from Baseline at
	weeks 2, 4, and 8
	 Achievement of an Overall Assessment of Erythema
	(0-3 scale) score of 0 or 1 at weeks 2, 4, and 8
	 Achievement of an Overall Assessment of Scaling
	(0-3 scale) score of 0 or 1 at weeks 2, 4, and 8
	• Achievement of an Overall Assessment of Erythema
	(0-3 scale) score of 0 at weeks 2, 4, and 8
	• Achievement of an Overall Assessment of Scaling
	(0-3 scale) score of 0 at weeks 2, 4, and 8
	• In subjects with a Baseline WI-NRS pruritus score
	of \geq 4, achievement of a \geq 4-point improvement from
	Baseline in WI-NRS pruritus score at weeks 2, 4,
	and 8
	• Change from Baseline in DLQI at weeks 2, 4, and 8
	• Change from Baseline in BSA affected at week 8
	• A 2-grade improvement in IGA from Baseline

Statistical Considerations:	There are approximately 184 subjects planned for this study; randomized 2:1 to ARQ-154 foam 0.3% : vehicle
	QD, stratified by study site and baseline disease severity.
	A sample size of 184 subjects will provide approximately 90% power to detect an active response of at least 55.8%, assuming 159 (86%) subjects complete the study and a vehicle response of 30%, based on two-group X^2 test of equal proportions (without continuity correction, using a 2-sided alpha of 0.10).

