5.9.1 Emergency Unblinding

Treatment assignment should remain blinded unless the knowledge is necessary to determine emergency medical care, as determined by the Investigator. Emergency unblinding will be done using the study IWRS system in consultation with the Medical Monitor and the Sponsor's CMO. Blinding of study treatment is critical to the integrity of this clinical trial and therefore, if a subject's treatment assignment is disclosed to the Investigator, the subject will have the IP discontinued.

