6.1 Statistical Methods

The methodology presented below is a summary of the more detailed analysis plan that will be presented in the Statistical Analysis Plan (SAP). The SAP will be finalized before the database is locked and unblinded. Any changes to the methods described in the final SAP will be described and justified in the clinical study report.

All statistical processing will be performed using SAS[®] (Version 9.4 or later) unless otherwise stated.

Descriptive statistics will be used to provide an overview of the efficacy, safety and pharmacokinetic results. For categorical parameters, the number and percentage of subjects in each category will be presented. The denominator for percentage will be based on the number of subjects appropriate for the purpose of analysis. For continuous parameters, descriptive statistics will include n (number of subjects), mean, standard deviation (SD), median, minimum, and maximum.

P-values of less than 0.10 will be considered statistically significant based on a two-sided test unless otherwise specified. No adjustments for multiplicity are planned.

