6.1.1 Determination of Sample Size

A sample size of approximately 184 subjects are planned for the study.

The randomization scheme will be 2:1 (ARQ-154 foam 0.3% QD: matching vehicle QD). Randomization will be stratified by site and baseline disease severity (IGA = 3 or IGA = 4). Approximately 121 subjects will receive ARQ-154 foam 0.3% QD; approximately 63 subjects will receive vehicle foam QD.

A sample size of 184 subjects will provide approximately 90% power to detect an active response of at least 58.5%, assuming 159 subjects complete the study and a vehicle response of 30%, based on two-group X^2 test of equal proportions (without continuity correction), using a 2-sided alpha of 0.10.

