6.3 Efficacy Evaluation

6.3.1 Primary Efficacy Endpoint

The primary efficacy variable in this study is success in Investigator Global Assessment (IGA) of disease severity, defined as an IGA score of 'Clear' or 'Almost Clear' plus a 2-grade improvement from Baseline at Week 8.

The primary endpoint will be analyzed using a Cochran-Mantel-Haenszel test stratified by the stratification factors study site and baseline disease severity. Statistical significance will be concluded at the 5% significance level (2-sided).

Missing IGA scores will be imputed using multiple imputation.

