7.4.1 Verification of Blinding

The treatment assignments for all enrolled subjects will be unblinded only after the conclusion of the study. Specifically, the blind will be broken only after all data are verified, entered into the database, and validated; subject evaluability assessments are performed and entered into the database; and the database is locked.

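### The primary test level (5%) contradicts the sizing alpha (0.10), neither stated active rate gives the stated 90% power, and the WI-NRS responder subset has two baseline thresholds

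*Protocol*

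**What the plan says.** **Primary significance level.** Protocol section 6.1 sets a general level: "P-values of less than 0.10 will be considered statistically significant based on a two-sided test unless otherwise specified". Section 6.3.1 then sets a level for the primary endpoint: "Statistical significance will be concluded at the 5% significance level (2-sided"). The sample size in section 6.1.1 is derived "using a 2-sided alpha of 0.10", and the synopsis uses the same 0.10.

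**Active response rate.** The synopsis claims "approximately 90% power to detect an active response of at least 55.8"%. Section 6.1.1 makes the same claim of about 90% power with 58.5%. Both assume 184 subjects, 159 completers, 30% response on vehicle, and a two-group chi-square test without continuity correction.

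**WI-NRS responders.** The synopsis and sections 6.3.2 and 6.3.3 restrict the 4-point responder analysis to subjects with a baseline score of at least 4. They list it twice, as a secondary and as an exploratory endpoint. Section 6.5.1 describes a 4-point responder analysis at the same weeks with the same stratified Cochran-Mantel-Haenszel (CMH) test. It requires a baseline score of at least 6 and refers the reader to the secondary endpoints.

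**Timing and blinding.** Section 6.1.3 plans one non-binding futility look at the first 60 randomized subjects, with accrual continuing, and says that "only sponsor staff responsible for planning further development in the seborrheic dermatitis program will be provided with results". Section 6.1 says: "The SAP will be finalized before the database is locked and unblinded". Section 7.4.1 says: "The treatment assignments for all enrolled subjects will be unblinded only after the conclusion of the study".

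**The concern.** A primary endpoint should have one significance level, and the power statement should use it. Here the test is at 5% and the sizing at 0.10, so the power described is not the power of the test that will be run. The two active rates make the design target itself ambiguous. A result that falls between the two critical values could be read as success or failure depending on the section cited.

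The WI-NRS conflict changes who is in the analysis. With baseline 4 or 5, a 4-point improvement means reaching 0, or at most 1. Including or excluding these subjects therefore changes both the denominator and how hard the response is to achieve.

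The interim look makes it useful to settle these points by a given date. If they were resolved after sponsor staff had seen comparative results, the sponsor would find it harder to show that the choice was made without that knowledge.

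**Working it through.** **Inputs from the protocol (synopsis and 6.1.1).** 159 completers; 2:1 allocation, hence 106 active and 53 vehicle; vehicle rate 0.30; active rate 0.558 or 0.585; uncorrected chi-square test; two-sided alpha 0.10 as sized, 0.05 as tested in 6.3.1.

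**Formula.** Let p̄ = (53 × 0.30 + 106 × p)/159, SE0 = √[p̄(1 − p̄)(1/53 + 1/106)] and SE1 = √[0.30 × 0.70/53 + p(1 − p)/106]. Power = Φ[(p − 0.30 − z × SE0)/SE1], with z = 1.645 for alpha 0.10 and 1.960 for 0.05.

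**Step 1: the plan's own figure, alpha 0.10.**
- p = 0.558: p̄ = 0.472, SE0 = 0.0840, SE1 = 0.0793. (0.258 − 1.645 × 0.0840)/0.0793 = 1.51, so power is 93.5%.
- p = 0.585: p̄ = 0.490, SE0 = 0.0841, SE1 = 0.0791. (0.285 − 1.645 × 0.0841)/0.0791 = 1.85, so power is 96.8%.

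Neither reproduces about 90%.

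**Step 2: the level in 6.3.1, alpha 0.05.**
- p = 0.558: (0.258 − 1.960 × 0.0840)/0.0793 = 1.18, so power is 88.1%.
- p = 0.585: (0.285 − 1.960 × 0.0841)/0.0791 = 1.52, so power is 93.6%.

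| Active rate | Power, alpha 0.10 | Power, alpha 0.05 |
|---|---|---|
| 55.8% (synopsis) | 93.5% | 88.1% |
| 58.5% (6.1.1) | 96.8% | 93.6% |

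**Step 3: the active rate that gives 90% power.** Solving the formula for p gives 54.0% at alpha 0.10 and 56.6% at 0.05. The synopsis rate lies between them; the 6.1.1 rate lies above both.

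**Step 4: sensitivity.**
- Scaling the 121:63 split in 6.1.1 to 159 completers (105:54) gives 93.6% and 88.3% at 55.8%.
- Exact binomial enumeration at 106:53 gives 93.5% and 87.9% at 55.8%.
- Counting all 184 subjects (121:63) moves further from 90% at alpha 0.10: 96.2% and 98.4% for the two rates.
- About 90% at 55.8% appears only under inputs the text does not state: a continuity correction at 0.10 (90.9%), which both passages exclude, or alpha 0.05 with unpooled variance (90.2%).
- For 58.5%, the closest is alpha 0.05 with a continuity correction (91.0%).

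**Step 5: the decision zone.** With 30% observed on vehicle, the smallest significant difference d solves d = z × √[p̄(1 − p̄)(1/53 + 1/106)], with p̄ evaluated at 0.30 and 0.30 + d.
- Alpha 0.10: 1.645 × 0.0821 = 0.135.
- Alpha 0.05: 1.960 × 0.0827 = 0.162.

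Differences from about 13.5 to 16.2 points succeed under one level and fail under the other.

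**Step 6: WI-NRS.** The two descriptions share the 4-point criterion, the weeks (2, 4 and 8), the test and its strata. They differ in the baseline cut-off, ≥4 or ≥6. The effect depends on how many subjects score 4 or 5 at baseline, which the protocol does not give, so no size is attached.

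**The case against.** **On alpha.** The general 0.10 in section 6.1 yields where another level is specified, and 6.3.1 specifies one. That stands: 6.1 and 6.3.1 do not conflict, and the written decision rule for the primary test is 5%. What remains is the mismatch between that rule and the 0.10 used to size the same endpoint.

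**On the interim.** A reader might infer that the sponsor will settle alpha or the itch subset after seeing unblinded data. The protocol does not support that. Section 6.1 sets only a latest date for the SAP, which may well precede the look. Section 6.1.3 speaks of results without saying that they are released by arm; comparative release is an inference from a futility rule in a vehicle-controlled trial. No passage says that the recipients have a role in the SAP. Section 6.1.3 does restrict access, and further separation is commonly set out in an SAP or interim charter. This objection largely stands, so the timing point is minor.

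**On section 7.4.1.** It might be read as forbidding the look. Section 6.1.3 can be taken as a specific exception. Section 7.4.1 is equally silent on the emergency route in 5.9.1: "Treatment assignment should remain blinded unless the knowledge is necessary to determine emergency medical care". This is a gap in wording and not a bar.

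**Conclusion.** Two contradictions are firm, and both matter at the final analysis whether or not an interim is run.

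1. The primary endpoint is tested at 5% but sized at 0.10, with two different active rates, and neither rate gives about 90% power as described. The choice of alpha is worth 5.4 points of power at 55.8% (93.5 − 88.1) and 3.2 points at 58.5% (96.8 − 93.6), and it decides any observed difference between about 13.5 and 16.2 points.
2. The WI-NRS responder subset has two baseline thresholds, and the endpoint sits in two tiers.

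The figures rest on 159 completers at 106:53, a 30% vehicle rate and an unstratified chi-square test, as in the plan's own sizing. The primary analysis is a stratified CMH test with multiple imputation, so they are approximate for it.

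The trial is not shown to be underpowered: the lowest of the four power values is 88.1%. The documents do not show which alpha or which active rate was intended. The non-binding futility look does not itself inflate type I error, and no bias from it is claimed. It only supplies a sensible date by which to close these points.

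**What to change.** - **Primary endpoint:** state one alpha and one active response rate in the synopsis, 6.1.1 and 6.3.1, and restate the power to match. The sample size stays at 184.
- **WI-NRS:** state one baseline threshold in the synopsis, 6.3.2, 6.3.3 and 6.5.1, and list the endpoint once, as either secondary or exploratory.
- **Minor clarification:** require in 6.1 that these choices are closed and the SAP signed before the interim unblinding. State in 6.1.3 that recipients of the results take no part in SAP decisions. Name the futility look as an exception in 7.4.1.

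The cost is wording, plus an earlier SAP sign-off. Any planner who receives interim results would have to hand over a role in the SAP. Visits, the futility rule and what planners may see are unchanged.

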6.1.4 Background and Demographic Characteristics

Demographic and baseline disease characteristics and vital sign information will be summarized descriptively for all randomized subjects.

6.1.5 Study Disposition

Number of subjects randomized, receiving IP, completing study, and withdrawing prematurely (with reason for withdrawal) will be summarized by treatment group.

6.1.6 Protocol Deviations and Eligibility Deviations

The number of subjects with important protocol deviations and/or eligibility deviations will be summarized in categories by treatment group.

6.1.7 Investigational Product Compliance

The number of IP applications by each subject based on diary data will be summarized using descriptive statistics.

The amount of IP used by each subject based on can weight will be summarized by treatment using descriptive statistics.

IP dose compliance will be calculated based on number of applications by the expected number (amount) of IP for each subject. Compliance will be summarized descriptively by treatment group. Amount of IP (weight) used will also be summarized.

6.2 Study Objective

6.2.1 Primary Objective

To assess the safety and efficacy of ARQ-154 foam 0.3% administered QD vs vehicle x 8 weeks in adults with seborrheic dermatitis.

6.3 Efficacy Evaluation

6.3.1 Primary Efficacy Endpoint

The primary efficacy variable in this study is success in Investigator Global Assessment (IGA) of disease severity, defined as an IGA score of 'Clear' or 'Almost Clear' plus a 2-grade improvement from Baseline at Week 8.

The primary endpoint will be analyzed using a Cochran-Mantel-Haenszel test stratified by the stratification factors study site and baseline disease severity. Statistical significance will be concluded at the 5% significance level (2-sided).

Missing IGA scores will be imputed using multiple imputation.

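### The primary test is set at two-sided 5%, but the trial is sized at two-sided 10%, with two different active rates and a 90% power that reproduces for neither

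*Protocol*

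**What the plan says.** Four places in the protocol bear on this.

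- **Section 6.3.1 (primary endpoint):** "Statistical significance will be concluded at the 5% significance level (2-sided"). The test is a Cochran-Mantel-Haenszel test stratified by site and baseline severity, with multiple imputation of missing IGA scores.
- **Section 6.1 (general methods):** "P-values of less than 0.10 will be considered statistically significant based on a two-sided test unless otherwise specified".
- **Section 6.1.1 (sample size):** "approximately 90% power to detect an active response of at least 58.5" percent, with 159 completers, a 30% vehicle rate and a two-group chi-square test "without continuity correction), using a 2-sided alpha of 0.10".
- **Synopsis, Statistical Considerations:** "approximately 90% power to detect an active response of at least 55.8" percent, with the same 184 subjects, 159 completers, vehicle rate and test, "without continuity correction, using a 2-sided alpha of 0.10".

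No section says why the comparison is planned at one level and tested at another, or why the active rate differs between the two power statements.

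**The concern.** The closing words of the Section 6.1 sentence allow an exception, and Section 6.3.1 supplies one. On its face, then, the primary test runs at 5%. The conflict is with the sample-size text. The only two power statements are at 0.10, so the protocol gives no power for the test that Section 6.3.1 prescribes. If 10% was intended throughout, the 5% sentence is wrong instead.

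The two power statements also contradict each other on the active rate, and both claim about 90%.

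Two things are at stake. A reader cannot tell what power the primary test has. And if 10% was the sponsor's intention, a Week 8 p-value between 0.05 and 0.10 would be declared a failure under Section 6.3.1. Settling that after results are known would look driven by the data.

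**Working it through.** **Inputs.** Vehicle rate p_v = 0.30 and 159 completers (Synopsis and 6.1.1). Allocation 2:1 (6.1.1), so n_a = 106 and n_v = 53. Active rate p_a = 0.558 (Synopsis) or 0.585 (6.1.1). Two-sided alpha 0.10 (z = 1.645; power statements) or 0.05 (z = 1.960; 6.3.1). Chi-square without continuity correction, as both power statements specify.

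**Formula.**

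power = Φ{ [ (p_a − p_v) − z·SE0 ] / SE1 }

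SE0 = √[ p̄(1 − p̄)(1/n_a + 1/n_v) ], with p̄ = (n_a·p_a + n_v·p_v)/(n_a + n_v)

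SE1 = √[ p_a(1 − p_a)/n_a + p_v(1 − p_v)/n_v ]

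**Step 1: the protocol's own figures, at alpha 0.10.**

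- Synopsis, 55.8%: p̄ = 0.472, SE0 = 0.0840, SE1 = 0.0793. (0.258 − 1.645 × 0.0840)/0.0793 = 1.51, giving **93.5%**.
- Section 6.1.1, 58.5%: p̄ = 0.490, SE0 = 0.0841, SE1 = 0.0791. (0.285 − 1.645 × 0.0841)/0.0791 = 1.85, giving **96.8%**.

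These exceed the claimed 90% by 3.5 and 6.8 points.

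**Step 2: the same design at the 5% of Section 6.3.1.**

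- 55.8%: (0.258 − 1.960 × 0.0840)/0.0793 = 1.18, giving **88.1%**.
- 58.5%: (0.285 − 1.960 × 0.0841)/0.0791 = 1.52, giving **93.6%**.

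**Step 3: does another reading rescue the 90%?**

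| Variant | 55.8%, α 0.10 | 55.8%, α 0.05 | 58.5%, α 0.10 | 58.5%, α 0.05 |
|---|---|---|---|---|
| Base case, 106:53 | 93.5% | 88.1% | 96.8% | 93.6% |
| Exact binomial enumeration, 106:53 | 93.5% | 87.9% | 96.8% | 93.4% |
| Completers split 105:54 (near 121:63) | 93.7% | 88.4% | 96.9% | 93.8% |
| Unpooled variance, 106:53 | 94.6% | 90.2% | 97.5% | 95.0% |
| Continuity-corrected, 106:53 | 90.9% | 84.1% | 95.3% | 91.0% |
| All randomised, 121:63 | 96.3% | 92.6% | 98.4% | 96.5% |

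At 0.10, only the continuity-corrected test with 55.8% comes near 90%, and both power statements exclude that correction. In the base case, 90% power is reached at an active rate of 54.0% (alpha 0.10) or 56.6% (alpha 0.05). The 58.5% rate gives 90% only at a two-sided alpha of about 0.029, which appears nowhere in the protocol. The Synopsis rate lies nearer to 90% at 0.05 than at 0.10.

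**Step 4: how often would the choice of alpha change the conclusion?** By exact enumeration at 106:53 with a true vehicle rate of 30%, the chance that p falls between 0.05 and 0.10 is the power at 0.10 minus the power at 0.05:

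- true active rate 55.8%: 0.935 − 0.879 = 5.6%
- 58.5%: 0.968 − 0.934 = 3.4%
- 45% (my assumption, for a weaker effect than planned): 0.573 − 0.443 = 13.0%

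**Step 5: completers needed for 90% at 2:1.** For 55.8%: 138 at 0.10 and 171 at 0.05. For 58.5%: 114 at 0.10 and 141 at 0.05. At the planned completion of 159/184 = 86.4%, 171 completers means 171/0.864 ≈ 198 randomised.

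**The case against.** The best defence has three parts.

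1. **The decision rule is determinate.** Section 6.1 allows exceptions and Section 6.3.1 makes one. This stands: those two sections do not contradict each other, and 5% is the likeliest reading. It does not reach the power statements, which plan the same comparison at 0.10.

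2. **The practical effect is small.** With 159 completers the 5% test has 88.1% or 93.6% power at the stated rates. At 0.10 the protocol understates its power. No reading leaves this proof-of-concept trial materially short of subjects. This also stands, and it is why no change in size is proposed.

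3. **The errors may be clerical.** The 58.5% could be 55.8% with digits transposed, and the 0.10 could be a slip for 0.05, since 55.8% at 0.05 gives 88.1%. Both are plausible and neither can be proved from the protocol. If both are true, Section 6.3.1 is right and the errors sit in the sample-size text, but that text still needs correcting.

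It could be added that the chi-square only approximates the stratified test with imputation. That is true, but the 90% is claimed for the chi-square, and it is against the chi-square that it fails.

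**Conclusion.** The concern holds. The prescribed 5% primary test has no stated power. The two power statements, both at 10%, disagree on the active rate. Neither reproduces its 90% at its own alpha (93.5% and 96.8%). At 5% the power is 88.1% for 55.8% and 93.6% for 58.5%.

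These figures assume an unstratified, uncorrected chi-square on 159 completers split 106:53 with a 30% vehicle rate. They do not model the site and severity strata or the imputation variance. The conclusion does not depend on the exact split, and exact enumeration agrees.

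The correction is required because the sample-size figures are wrong as written and leave doubt about the intended threshold for the primary endpoint. The trial size itself is not at fault.

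**What to change.** State one two-sided alpha for the primary test in the Synopsis, Section 6.1.1 and Section 6.3.1. Use one active rate in the Synopsis and Section 6.1.1, and give the power at that alpha and rate.

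- **Smallest change (5% kept):** leave Section 6.3.1 as it is, replace 0.10 with 0.05 in both power sentences, and state about 88% power if the rate is 55.8%, or about 94% if it is 58.5%, with 159 completers. The 0.10 default in Section 6.1 can stay for other tests if the primary test is named there as the exception.
- **If 10% is intended:** delete the 5% sentence in Section 6.3.1 and state about 93% (55.8%) or about 97% (58.5%).

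Make the change before the futility analysis of Section 6.1.3, which takes place after the first 60 randomised subjects have had the opportunity to complete the Week 8 assessment. Its results go to sponsor planning staff, and a threshold settled afterwards would be harder to defend.

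The cost is wording in three places and a cross-reference in Section 6.1, with no extra subjects. Keeping 5% with 55.8% means stating 88% in place of 90%. A full 90% there would need about 171 completers (about 198 randomised), which I do not propose. With 58.5%, 141 completers suffice.
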